11.4.2.2. Secondary Analyses

Secondary endpoints of the change from baseline in NRS Annoyance score, NRS Loudness score, TFI overall score, TFI subscale scores, PGIC, and SF-12 will be summarized descriptively by treatment group and visit.

There will be no adjustment of multiplicity across secondary endpoints.

11.4.2.2.1. Additional Responder Analyses

The following additional responder definitions will also be derived for Weeks 12 and 16:

- Week 12 responder #1: achieving at least a 13-point reduction from baseline in the TFI overall score at Weeks 8 and 12
- Week 12 responder #2: achieving at least a 13-point reduction from baseline in the TFI overall score at Weeks 4, 8, and 12
- Week 16 responder #1: achieving at least a 13-point reduction from baseline in the TFI overall score at Weeks 12 and 16
- Week 16 responder #2: achieving at least a 13-point reduction from baseline in the TFI overall score at Weeks 8, 12, and 16
- Week 16 responder #3: achieving at least a 13-point reduction from baseline in the TFI overall score at Weeks 4, 8, 12 and 16

These additional responder secondary endpoints will be analyzed in the same manner as the primary analysis as described in Section 11.4.2.1.

11.4.2.2.2. Continuous Endpoint Analyses

The change from baseline in NRS Loudness, NRS Annoyance, TFI Total score, each TFI subscale score, and SF-12 will each be analyzed using a linear mixed-effects model with treatment, study day, treatment-by-study day interaction, study site, baseline TFI overall score, and duration of tinnitus as fixed effects. The unstructured covariance model will be used. Least-square adjusted means, the estimated difference in adjusted means between treatment groups and associated 95% CIs will be provided.

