
Statistical Methods:
 
Sample Size Justification:
 
The primary endpoint is the percentage of responders, where response is defined as achieving at least a 13-point reduction from baseline in the TFI total score at both Weeks 4 and 8. It was observed from the previous study that the response rate for OTO-313 (0.32 mg) was 43%, and 13% for placebo. Based on these results, the assumed rate of response for OTO-313 is 43% and 18% for placebo, which is the 13% observed response rate in previous study plus 5% inflation for potential placebo response.
 
Assuming a 2-sided test and level of significance of 0.05, 60 subjects in the placebo group and 60 subjects in the OTO-313 group will provide approximately 85% power to detect a treatment difference in favor of OTO-313. It is also assumed that an observed discontinuation rate of 15% will be observed, hence the total sample size for this 2-arm study is planned to be 140 subjects, 70 subjects per arm. These sample size calculations were conducted using EASTv6.5 software with a test for a difference in proportions between two groups.
 
Analyses:
 
The primary endpoint, analyzed using the common risk difference between treatment groups, will be tested using a Mantel-Haenszel test controlling for duration of tinnitus and baseline TFI score at Week 8. The 95% confidence intervals (CI) around the common risk difference will be provided. The risk difference in responses rates will also be compared between treatment groups at Weeks 12 and 16 as secondary analyses.
 
The change from baseline in NRS Loudness, NRS Annoyance, TFI total score, each TFI subscale score, and SF-12 will each be analyzed using a linear mixed-effects model with treatment, study day, treatment-by-study day interaction, gender, and tinnitus duration as fixed effects. The unstructured covariance model will be used. Least-square adjusted means, the estimated difference in adjusted means between treatment groups and associated 95% CIs will be provided. Comparisons between treatment groups will be conducted at each post-baseline visit as secondary analyses.
 
The results of the PGIC will be analyzed using a Cochrane-Mantel-Haenszel mean score test controlling for baseline TFI score and duration of tinnitus. This will be done to compare OTO-313 with placebo.
 
Adverse events, audiometry, tympanometry, otoscopic, and C-SSRS safety endpoints will be summarized descriptively. Changes in vital signs and laboratory parameters will be summarized descriptively.
	

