4. STUDY POPULATION

4.1. General Considerations

Approximately 140 subjects will be enrolled at approximately 55 sites globally. Subjects will be eligible if they meet all of the following inclusion criteria and none of the exclusion criteria.

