5.2.3. Randomization Algorithm

Subjects will be randomized in a 1:1 ratio (OTO-313:placebo) of treatment groups using a permuted block randomization algorithm. Randomization is stratified by study site, duration of

tinnitus (≥ 2 to ≤ 6 months and > 6 to ≤ 12 months since onset) and by the average of the TFI score at Screening and Baseline (≥ 32 to ≤ 53 points, ≥ 54 to ≤ 100 points).

The randomization process will be deployed via IRT which is accessible 24 hours a day to authorized users. The subject's randomization number will determine the randomized treatment assignment. Investigational product kits will be labeled with a unique kit number using a separate and independent randomization algorithm. Numbered kits will be dispensed based on the treatment assignment.

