11. STATISTICAL METHODS

11.1. Introduction

Detailed methodology for summary and statistical analyses of the data collected in this study will be documented in a Statistical Analysis Plan (SAP). The SAP may appropriately modify the analyses specified in the protocol, as necessary.

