11.4. Statistical Analyses

11.4.1. General

There will be two sets of analyses. The Primary analyses will be conducted after all subjects complete Week 8 of the study, with all planned analyses to be conducted with all data collected in the database at time of database freeze. There will be a final analysis conducted once all subjects complete Week 16 of the study, to include all data collected from all subjects across all time points.

All data collected will be summarized descriptively. Descriptive statistics for continuous data are number of subjects, mean, standard deviation, median, minimum, and maximum values. Descriptive statistics for categorical variables will include number of observations and percentages.

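### The Synopsis and Section 11.4.2.2.2 give different mixed models for the same continuous secondary endpoints, and neither includes the outcome's own baseline for the NRS scores, TFI subscales or SF-12

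*Combined protocol and SAP*

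**What the plan says.** Both places describe one analysis: change from baseline in NRS loudness, NRS annoyance, TFI total, each TFI subscale and SF-12, by a linear mixed-effects model with unstructured covariance.

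- Section 11.4.2.2.2 lists "treatment, study day, treatment-by-study day interaction, study site, baseline TFI overall score, and duration of tinnitus as fixed effects".
- The Synopsis (Statistical Methods, Analyses) lists "treatment, study day, treatment-by-study day interaction, gender, and tinnitus duration as fixed effects".

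The Synopsis does use baseline TFI in its other two efficacy tests; for PGIC it specifies a "mean score test controlling for baseline TFI score and duration of tinnitus". Randomization (Section 5.2.3) is stratified by site, tinnitus duration and a two-level TFI category defined "by the average of the TFI score at Screening and Baseline". Gender is not a stratification factor.

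On scale, Section 4.1 states: "Approximately 140 subjects will be enrolled at approximately 55 sites globally". On timing, Section 11.4.1 places the first analysis after all subjects reach Week 8, "with all planned analyses to be conducted with all data collected in the database at time of database freeze". Section 11.1 adds: "The SAP may appropriately modify the analyses specified in the protocol, as necessary". No SAP text that chooses between the two models is included.

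**The concern.** A prespecified analysis should lead to one estimate and one interval for each endpoint. Here a statistician following the Synopsis and one following Section 11 would fit different models to the same data, and the difference is not cosmetic: one model has up to 54 site parameters and a baseline covariate, the other has neither. Because "There will be no adjustment of multiplicity across secondary endpoints", nothing else in the plan disciplines how these results are chosen or read.

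The second issue is common to both lists. The strongest available predictor of a follow-up score is usually the same score before treatment. Analysing change does not stand in for adjusting on it, because subtraction fixes the baseline slope at 1 instead of estimating it. Baseline TFI is a partial proxy for the other scores. What is at stake is the width of the secondary intervals and some correction for chance baseline imbalance, not the validity of the randomized comparison.

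**Working it through.** **1. The two lists side by side**

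| Term | Synopsis | Section 11.4.2.2.2 |
|---|---|---|
| Treatment, study day, interaction | yes | yes |
| Tinnitus duration | yes | yes |
| Gender | yes | no |
| Study site | no | yes |
| Baseline TFI overall | no | yes |
| Own baseline: NRS ×2, TFI subscales ×8, SF-12 | no | no |
| Own baseline: TFI total | no | yes, if baseline TFI is continuous |

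The last row is conditional. Section 11.4.2.1 uses the same phrase for baseline TFI as a control in a Mantel-Haenszel test, which needs categories, and the randomization factor is a two-level split. Section 11.4.2.2.2 does not say which form it means.

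**2. The plan's own figure.** The documents give no power or precision figure for the continuous endpoints. The only power statement (Section 11.5) is for the primary responder endpoint: 43% v 18%, 60 per arm, two-sided 0.05. With pooled variance, z = [0.25√60 − 1.96√(2 × 0.305 × 0.695)] / √(0.43 × 0.57 + 0.18 × 0.82) = (1.936 − 1.276)/0.627 = 1.054, so power is 85.4%. This reproduces the stated 85% or so, and nothing below changes it.

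**3. Cost of site as a fixed effect.** 140/55 = 2.5 subjects per site. Assumptions: 120 or 140 subjects, 55 sites, permuted blocks of 2 or 4 within site × duration × TFI category (55 × 2 × 2 = 220 cells), and no true site differences. For a given allocation, the variance ratio is the residual sum of squares of the treatment indicator after duration and TFI category, divided by the same quantity after also removing site. Medians over 400 simulated allocations per case:

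| N | Even recruitment, block 2 / 4 | Uneven recruitment, block 2 / 4 |
|---|---|---|
| 140 | 1.32 / 1.45 | 1.22 / 1.29 |
| 120 | 1.41 / 1.56 | 1.28 / 1.35 |

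The variance rises by 22-56%. Since √1.22 = 1.105 and √1.56 = 1.249, intervals are about 11-25% wider. The reason is that 14-30% of subjects fall in sites with only one arm, which add nothing to a within-site comparison.

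**4. Gain from own baseline.** The documents give no correlations or SDs, so these are assumed. Let r be the correlation of own baseline with follow-up, k that of own baseline with baseline TFI, and kr that of follow-up with baseline TFI. Let s be follow-up SD divided by baseline SD, with baseline SD = 1. Residual variance of the change score:

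- no baseline term: 1 + s² − 2rs
- baseline TFI only: 1 + s² − 2rs − k²(1 − rs)²
- baseline TFI plus own baseline: s²(1 − r²)

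Example, s = 1, r = 0.5, k = 0.5: 1.000, 0.9375 and 0.750. The cut from adding own baseline to the Section 11.4.2.2.2 covariates is 1 − 0.750/0.9375 = 20%.

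Example, s = 1.2, same r and k: 1.240, 1.200 and 1.080. The cut is 1 − 1.080/1.200 = 10%.

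| Cut at r = 0.3 / 0.5 / 0.7 | s = 1 | s = 1.2 | s = 1.3 |
|---|---|---|---|
| v Section 11.4.2.2.2, k = 0.5 | 29 / 20 / 12% | 19 / 10 / 3% | 15 / 7 / 1% |
| v Section 11.4.2.2.2, k = 0.8 | 16 / 11 / 6% | 10 / 5 / 1% | 8 / 3 / 0.3% |
| v Synopsis | 35 / 25 / 15% | 24 / 13 / 3% | 20 / 9 / 1% |

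At s = 1, k = 0.8 and r = 0.7, lowering the follow-up-to-TFI correlation by 0.1 leaves a cut of only 0.4%. High k is the plausible case for subscales, which are components of the TFI.

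**The case against.** The best defence is that the conflict is editorial. Sections 11.4.2.1, 11.4.2.2.2 and 11.4.2.2.3 all use site, baseline TFI and duration, matching the randomization factors. The Synopsis drops site from all three analyses, so it looks like a summary out of step with the body. Section 11.1 also lets the SAP revise the models, and these are Phase 2 secondary endpoints. This explains how the mismatch may have arisen, but it does not remove it: the Synopsis adds gender, which an abbreviated list would not do, and no text gives Section 11 precedence. Permission to modify is not a choice between two lists.

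It is also fair to say that omitting own baseline from a change-score model is not an error, and that the gain depends on the SD ratio. Eligibility requires TFI of at least 32 at Screening and Baseline, which could narrow baseline spread relative to follow-up and shrink the gain. That objection stands, and the ranges above reflect it.

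A reader might infer that fixed site effects always lose precision. The 22-56% assumes no true site differences; real ones would offset some of the cost.

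**Conclusion.** The mismatch is established from the text alone. The absence of own baseline is equally clear for both NRS scores, the TFI subscales and SF-12. For TFI total it is certain in the Synopsis, and in Section 11.4.2.2.2 it depends on the form in which baseline TFI enters.

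The sizes are conditional. Fixed site effects cost about 22-56% in variance with no true site differences, and less otherwise. Adding own baseline to the Section 11.4.2.2.2 model cuts residual variance by about 6-29% with equal SDs (r = 0.3-0.7, k = 0.5-0.8) and by about 0-19% with a follow-up SD 1.2-1.3 times baseline. For TFI subscales it may be near nil.

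A reader might go further and conclude that the secondary estimates are biased or the primary result is compromised. The documents do not support that: treatment is randomized, so either model gives an unbiased comparison, and the primary responder test is a separate analysis. Nor do they show that anyone intends to choose between models after seeing data. The point is worth correcting because the remedy is nearly free.

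**What to change.** Write one model, identically, in the Synopsis and Section 11.4.2.2.2, and carry it into the SAP before the Week 8 database freeze:

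- treatment, scheduled visit and treatment-by-visit;
- the outcome's own baseline, as a continuous covariate;
- baseline TFI overall, kept and stated to be continuous (for TFI total this and own baseline are one term);
- tinnitus duration;
- gender in both places or in neither.

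Do not enter about 55 sites as fixed effects at about 2.5 subjects per site. Use a random site effect, pooled sites or no site term, and say which and why.

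The cost is wording. All the baseline scores are already scheduled before dosing, and each model gains one covariate, or none for TFI total where baseline TFI is already there as a continuous term. No visit, subject or sample-size figure changes.

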11.4.2.2.3. Categorical Endpoint Analyses

The results of the PGIC will be analyzed using a Cochrane-Mantel-Haenszel mean score test controlling for study site, baseline TFI score, and duration of tinnitus. This will be done to compare OTO-313 with placebo.

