10.2.2. Replacements

Subjects who discontinue participation in the study for any reason after dosing will not be replaced. The sample size was estimated to account for an assumed discontinuation rate of 15% by Week 8.

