11.2. Analysis Sets

The all enrolled set will include all subjects who sign an informed consent form.

The full analysis set (FAS) includes all randomized subjects, and they will be included in the group to which they were randomized.

The per-protocol analysis set (PP) includes all subjects in the full analysis set that provide TFI data at Weeks 4 and 8, and do not have any protocol deviations that may impact the outcome of the TFI overall score.

The safety analysis set includes all subjects who receive study treatment, and they will be included in the treatment group based on the treatment received.

The FAS and PP sets will be used for efficacy analyses. The safety analysis set will be used for all safety analyses.

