11.4.2. Efficacy Analyses

All efficacy endpoints will be summarized descriptively and analyzed using FAS. The primary endpoint will also be summarized descriptively and analyzed using PP.

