11.4.2.1. Primary Analyses

The primary endpoint is the percent of responders at Week 8, where subjects will be classified as responders if they achieve at least a 13-point reduction from baseline in the TFI overall score at both Weeks 4 and 8. The primary endpoint will be summarized descriptively by treatment group. The percentage of responders will be analyzed using the common risk difference between treatment groups and will be tested using a Mantel-Haenszel test controlling for study site, duration of tinnitus, and baseline TFI overall score. Specifically, comparison between OTO-313 and placebo will be made by testing the following hypothesis:

$$H_0: P_{\text{OTO-313}} = P_{\text{Placebo}} \text{ vs } H_A: P_{\text{OTO-313}} \neq P_{\text{Placebo}}$$

The primary analysis will be conducted for the comparison of OTO-313 and placebo, using a 2-sided test and an alpha level of 5%. The 95% confidence intervals (CI) around the common risk difference will also be provided.

Missing data for the primary endpoint will be imputed using a multiple imputation technique that will be described in detail in the SAP.

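### The PGIC test can use only subjects scored at the visit in question and comes with no between-group estimate or confidence interval, although the endpoint is assigned to the full analysis set

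*Combined protocol and SAP*

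**What the plan says.** Section 11.4.2 sets the analysis population: "All efficacy endpoints will be summarized descriptively and analyzed using FAS". Section 11.2 defines it: "The full analysis set (FAS) includes all randomized subjects". Section 10.2.2 says how many are expected to leave: "The sample size was estimated to account for an assumed discontinuation rate of 15% by Week 8".

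Section 8.4.4 describes the PGIC as seven categories scored from -3 to +3, with no baseline value. Section 11.4.2.2.3 gives its analysis: "The results of the PGIC will be analyzed using a Cochrane-Mantel-Haenszel mean score test", stratified by site, tinnitus duration and baseline TFI. It names no visit, no rule for a missing score, no between-group estimate and no interval. The synopsis adds none of these. Section 11.4.2.2 plans descriptive PGIC summaries by arm and visit.

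The other efficacy endpoints are specified more fully:

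- **Primary responder endpoint (11.4.2.1):** "Missing data for the primary endpoint will be imputed using a multiple imputation technique that will be described in detail in the SAP", and "The 95% confidence intervals (CI) around the common risk difference will also be provided".
- **Additional responder endpoints (11.4.2.2.1):** "These additional responder secondary endpoints will be analyzed in the same manner as the primary analysis".
- **NRS, TFI total, TFI subscales and SF-12 (11.4.2.2.2):** a linear mixed-effects model over study days with unstructured covariance, giving adjusted mean differences and 95% CIs.

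**The concern.** A mean score test compares the arms' average scores within strata at one time point, so a subject without a score at that time contributes nothing. Take a subject who reports no improvement at Week 4 and then leaves. That subject is absent from the Week 8, 12 and 16 comparisons, although the Week 4 answer is in the database and predicts the later ones. If leaving is related to how the subject is doing, those who remain are a selected group.

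The PGIC is the subject's own judgement of whether the tinnitus changed, and Section 2.2 names it in a secondary objective. A reader of the trial report will want to know how large the difference is and how precisely it is known. The planned test answers only whether the arms differ, and only among those still reporting.

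**Working it through.** **1. The plan's own figures.** Section 11.5 gives no figure for the PGIC, so the primary calculation is checked for context. With 43% against 18% and 60 per arm, the pooled rate is 0.305.

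- SE under the null = sqrt(2 x 0.305 x 0.695 / 60) = 0.0841.
- SE under the alternative = sqrt((0.43 x 0.57 + 0.18 x 0.82) / 60) = 0.0809.
- Power = Phi((0.25 - 1.96 x 0.0841) / 0.0809) = Phi(1.05) = 85.4%, matching the stated 85%.
- 60 / 0.85 = 70.6, so 71 per arm or 142 in total, close to the stated 140.

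**2. Who is in the Week 8 PGIC test.** 140 x 0.15 = 21 subjects gone, leaving 140 - 21 = 119. This assumes that nobody who stays misses a PGIC and that no early-termination score is counted as Week 8. The documents give no rate for Weeks 12 and 16.

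**3. How selection moves an observed-case difference.** Assume both arms share one PGIC distribution, with probabilities 0.03, 0.07, 0.12, 0.40, 0.20, 0.12 and 0.06 for scores -3 to +3. There is then no true difference. Scores of 0 or below have total probability 0.62 and contribute -0.35 to the mean; positive scores contribute +0.62. If a fraction p of an arm is missing, all of it from scores of 0 or below, the observed mean is

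(0.62 - 0.35 x (1 - p / 0.62)) / (1 - p).

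- p = 0.10 gives 0.363 and p = 0.20 gives 0.479, a spurious difference of 0.12.
- p = 0.05 gives 0.314 and p = 0.25 gives 0.548, a spurious difference of 0.23.
- Equal p in the two arms gives 0.

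The arm that loses more poor scorers looks better. This is a severe mechanism, chosen to show direction.

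**4. A milder mechanism with a true effect.** Simulated trials used 70 per arm, PGIC SD 1.3, a true Week 8 difference of about 0.59, a Week 4 to Week 8 correlation of 0.5 to 0.8, and dropout before Week 8 depending on the Week 4 PGIC (3,000 trials per setting). None of these inputs comes from the documents.

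- *Poor Week 4 scores drive dropout in both arms* (14-15% missing on OTO-313, 17-21% on placebo): the observed-case difference was 0.51 to 0.57, about 2% to 12% too small. At correlation 0.8 and the steeper dropout slope it was 0.520 against 0.588, and (0.588 - 0.520) / 0.588 = 11.6%. Placebo has more poor scorers to lose, so its observed mean rises more.
- *Poor Week 4 scores drive dropout on OTO-313 only* (14% against 15% missing, correlation 0.8): 0.72 against 0.575, and (0.72 - 0.575) / 0.575 = 25% too large. On similar inputs the excess was about 30%. Overall dropout is almost equal here, so similar dropout rates would not reveal it.
- *Using the Week 4 PGIC in both-arm settings:* the estimate returned to 0.58-0.59, with a standard error within about 3% of the observed-case one.

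**5. Scale.** With SD 1.3 and 60 per arm, the SE of a mean difference is 1.3 x sqrt(2 / 60) = 0.24. The errors in step 4 are then 0.068 / 0.24 = 0.28 SE in the example towards the null, and 0.145 / 0.24 = 0.60 SE in the example favouring OTO-313.

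**The case against.** Several counter-arguments have force.

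- **Early-termination scores.** Table 1 and Section 8.1.7 include the PGIC at early termination, and Section 10.2.1 encourages leavers to attend that visit. Some will have a score later than Week 4. This stands. However, Section 11 does not say whether such a score counts at a scheduled visit, and the test as written uses no score from an earlier visit.
- **Detail may sit elsewhere.** Section 11.1 defers detailed methods to a SAP that may modify the analyses, and no such text is in the document reviewed. That the test excludes unscored subjects is a property of the method, not a sentence in the protocol. This stands as a limit on certainty. Still, Section 11.4.2.1 expressly defers only the primary endpoint's imputation, with nothing comparable for the PGIC.
- **Choice of method.** A stratified mean score test is conventional for an ordinal scale, and the bias is usually a fraction of a standard error. Both are true. They argue for a low priority and for keeping the test, not against adding an estimate.

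Three stronger readings are tempting but unsupported:

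- A reader might infer that the PGIC is the only endpoint that loses early leavers. The SF-12 is scheduled after baseline only at Weeks 8 and 16, so a subject who leaves before Week 8 without an early-termination SF-12 has no outcome in its model either.
- A reader might infer that anyone with a missing PGIC is lost altogether. The exclusion is visit by visit.
- A reader might infer that the trial could not gauge the PGIC effect at all. The by-arm summaries allow a crude, unadjusted, observed-case difference.

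**Conclusion.** The point holds as a minor weakness in a secondary analysis. As written, the Week 8 PGIC comparison would rest on about 119 of 140 subjects, which is an observed-case set and not the full analysis set of Sections 11.2 and 11.4.2. It would give no prespecified between-group estimate or interval.

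The bias is usually modest, about 2% to 12% of the effect and towards the null. It can reach about 25% to 30% in favour of OTO-313 if poor responders leave mainly from that arm. These sizes depend on the assumed SD, effect, correlation and dropout mechanism. In the simulations dropout depended on the Week 4 score, which is observed. If it depended on later unobserved scores, a model using Week 4 could not be relied on to remove all the bias.

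A reader might infer that the trial's main result is at risk. It is not: the PGIC is secondary, Section 11.4.2.2 makes no multiplicity adjustment across secondary endpoints, and the primary endpoint has its own imputation.

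**What to change.** In Section 11.4.2.2.3, analyse the PGIC score (-3 to +3) at Weeks 4, 8, 12 and 16 with the repeated-measures mixed model of Section 11.4.2.2.2. The outcome is the score itself, because there is no baseline PGIC. Report the adjusted mean difference with 95% CI at each visit and keep the mean score test as a supportive analysis. State how an early-termination PGIC is assigned to a visit.

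The synopsis and Section 11 list different covariates for the mixed model, and different strata for the PGIC test (study site appears only in Section 11). Use whichever set is settled for the other continuous endpoints.

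Leave the primary endpoint's imputation model unchanged. Adding the PGIC to it would alter the primary analysis for the sake of a secondary endpoint.

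The cost is one more run of a model type already planned, plus the wording. The downside is that a seven-point scale is treated as numeric, which the mean score test already does by using the point scores. The model also assumes that missingness is explained by the observed scores and covariates, and it cannot recover subjects with no post-dose PGIC at all. Make the change before unblinding, so that the handling of missing scores cannot appear data-driven.
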